1. *Screening* We propose to employ a two stage screening process. The first phase is a village - based survey to identify children who are infected using rapid point of care testing (urine Circulating Cathodic Antigen (CCA)). CCA provides a highly sensitive and efficient means to screen children, with high sensitivity demonstrated in young children.^{18,19 20,21} Two stool samples (taken on consecutive days) will also be collected from every child who is CCA positive prior to the start of the study, at four weeks +/-1 week after treatment, and at 12 months post-treatment to provide a measure of infection intensity. Fecal smears will be prepared from each sample in duplicate applying the thick Kato-Katz technique for the detection of *S. mansoni*, *S. japonicum* and soil-transmitted helminths. Mean egg counts per gram of stool (epg) will subsequently be calculated and three intensity categories will be considered for *S. mansoni* and *S. japonicum* infection: light (1-99 epg), medium (100 – 399 epg) and heavy (>400 epg) as per World Health Organization Guidelines.²²

The second phase of screening will occur at the field laboratories in Palo, Leyte, The Philippines and in Lake Albert, Uganda. Prior to study enrollment, each child will undergo a physical exam and medical history to determine eligibility. Children who are not eligible based on severe malnutrition (WHZ < -3.0), severe anemia (hemoglobin < 7.0 g/dL) or chronic medical condition as defined by a disease lasting longer than three months and impacting a child's daily function or normal activities will be excluded at this stage.²³

1. *Study visit 1/Baseline.* After determination of eligibility, subjects will be enrolled following all screening assessments. Both field stations have a patient intake area with private areas for consenting and physical examinations. At this visit, a small blood drawing catheter will be placed to minimize the number of times children need to have a needle stick. Blood will be drawn for baseline morbidity studies (5 ml). In depth measures of nutritional status will be made, and children will be randomized to receive either 40 mg/kg or 80 mg/kg of Praziquantel either annually or six-monthly (4 arms).

In addition, children will be randomly split into two groups, half will have an extra 7 ml of blood drawn at the time of the morbidity studies (N=150) for immunologic studies and half will take part in pharmacokinetic studies (N=150, further details below).

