To test gut permeability and absorptive capacity, lactulose-mannitol solution (containing 250 mg/mL lactulose and 50 mg/mL mannitol in purified water) will be administered to study participants orally at a

dose of 2ml/kg up to a maximum of 20 ml. Prior to administration of the solution, the child will be fasted for 30 minutes. Breast feeding will continue. A urine bag will be strapped to ensure all the urine is collected. The first urine sample voided will be considered as baseline. A new bag will then be put in place to continue urine collection for 2 hours. Once collected, an aliquot of 2 ml of urine will be stored between 2°C and 8°C having added 2 drops of chlorhexidine. Two hours after ingestion of LM solution, the test will be stopped. If the child has not passed any urine, the test time will be extended until the next urine is voided.

Following the LM test, two doses of PZQ will be administered three hours apart. After receiving praziquantel, all children will stay at the study premises for 3-6 hours with a guardian monitoring side effects. After administration of the second dose of the study product, children will undergo ultrasound scan to determine presence or absence of any pathology related to schistosomiasis. The Niamey Protocol will be used to grade severity of disease.

The subset of children (approximately N=150) who will be randomly selected for PK sampling (four blood draws in total) children will stay at the premises for at least 6 – 8 hours after administration of the initial dose of praziquantel. At the time of discharge, children who will be found to be infected with soil-transmitted helminths will be treated with albendazole 200 mg (12 – 24 month old children) or albendazole 400 mg (children over age two). Blood Chemistry to ascertain renal and liver function will be repeated 6 – 8 hours after administration of the first dose of praziquantel, before discharge.

2. *Study Visit 2.* Stool will be collected 4 weeks (+/- 1 week) after treatment. Two stools will be collected on consecutive days to quantify egg counts by Kato Katz. Field workers will be responsible for picking up cups at this timepoint. No visit to the field laboratories will be required. Urine will be collected for CCA/CAA. Blood (7 ml) will be collected for the same subset of N=150 subjects for studies of immunological responses as at baseline.

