This sample size will give 80% power to detect differences in the secondary morbidity outcomes measures. We increase the estimated loss to follow up for these endpoints given they occur at six and 12 months following treatment. With 10% attrition, we will have 540 subjects at the 12 month follow up. As one example of the effect size we will detect for the key secondary outcome of weight-for-height z-score at 12 months, we will have 80% power to detect a difference in mean weight-for-height z-score between the six-monthly and 12-monthly dosing groups as low as 0.24 z-score, assuming a standard deviation of 1 and two-sided significance level 5% between children who received six-monthly praziquantel (either 40 mg/kg or 80 mg/kg) and children who received 12-monthly praziquantel (either 40 mg/kg or 80 mg/kg). A weight for age z-score difference of 0.23 is biologically relevant, particularly based on mitigation of only one cause of nutritional morbidity in this setting. For hemoglobin, we will be able to detect a difference of 0.29 g/dL using a standard deviation of 1.2, power of 80%, and functional sample size of 540.

For the PK study, 137 children from both sites (Uganda/Philippines) will be sampled. These are the numbers needed for 80% power to show a slope of the relationship between log CAA at 24 days and AUC is significant to $p < 0.05$. We will include 150 children to allow for loss to follow-up and enable sufficient power.

To assess immunological responses, assuming an SD of 0.9, the sub-study would require a sample size of 104 to achieve 80% power at 5% significance level for detecting difference in mean of $0.35\log_{10}$ cytokine response between the groups. We will recruit 150 children to allow for attrition.

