For the secondary outcomes assessed at 6 and 12 months (anthropometry and anemia), continuous outcomes will be compared between trial arms using linear regression, including the corresponding baseline measure as a covariate. Binary outcomes assessed at 6 and 12 months will be compared between trial arms using binary/logistic regression, including the corresponding baseline measure as a covariate. This will be done in order to improve the precision of the treatment effect estimate.

Due to the large sample size, no imbalance is expected between trial arms. Therefore, no further adjustment for baseline characteristics is planned for any outcome, unless there are significant differences demonstrated at baseline for key potential confounders.

We will pre-specify three key potential effect modifiers to be examined. These include site (Uganda versus the Philippines), age (12-30 months versus 31-47 months) and baseline intensity of infection (Low versus moderate/high). We will examine whether cure rate and egg reduction rate, as well as key measures of morbidity differ by these sub-groups. Effect modification will be tested by fitting interaction terms in regression models.

Full details, including shell tables will be included in a formal statistical analysis plan, to be finalized and reviewed before database lock.

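### No baseline-adjusted model is stated for the immune responses, although each sub-study child has a pre-treatment value, and the sub-study's 104 is a per-group number that 150 children in total do not meet

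*Combined protocol and SAP*

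**What the plan says.** Section 11.4 (Analysis Plan) limits the adjusted analysis as follows: "For the secondary outcomes assessed at 6 and 12 months (anthropometry and anemia), continuous outcomes will be compared" by linear regression with the matching baseline measure as covariate, with precision given as the reason. It then says that no other baseline adjustment is planned for any outcome, unless key potential confounders differ significantly at baseline. Details are left to a formal SAP, to be finalised before database lock.

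Immune responses are item 15 in section 11.1, labelled exploratory. No test or model is named for them. Their sampling is described in section 4.2.1:

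- At baseline, "half will have an extra 7 ml of blood drawn at the time of the morbidity studies (N=150) for immunologic studies".
- At 4 weeks, blood is taken from the same subset of 150 "subjects for studies of immunological responses as at baseline".
- The same subset is sampled again at 6 and 12 months.

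Section 11.2 sizes this sub-study: "assuming an SD of 0.9, the sub-study would require a sample size of 104 to achieve 80% power at 5% significance level", for a difference of 0.35 log10 in mean cytokine response between groups that it does not define. It continues: "We will recruit 150 children to allow for attrition". No baseline term and no correlation appear.

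**The concern.** The plan accepts that an outcome's own baseline value buys precision, and gives that benefit to outcomes measured in all 600 children. It does not extend it to an outcome measured in only 150, where between-child variation is large: the SD of 0.9 is about 2.6 times the difference sought (0.9 / 0.35 = 2.57). The pre-treatment sample is drawn from every child in the sub-study. If the follow-up comparison ignores it, stable differences between children stay in the error term.

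The sizing sentence adds a second problem. If 104 is a per-group number, recruiting 150 in total does not allow for attrition. The sub-study starts below its 80% target before any child is lost. Each visit's sample costs 7 ml of blood from a child under four, so using the data already collected is the least burdensome remedy.

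**Working it through.** **Inputs from section 11.2.** Difference d = 0.35 log10, SD = 0.9, significance level 5%, power 80%, stated size 104, planned total 150.

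**Assumptions.**
- The test is two-sided. This is not stated for the sub-study; the weight-for-height example in the same section has "assuming a standard deviation of 1 and two-sided significance level 5"%.
- The 150 children form two groups of 75. This fits the equal arms but is not stated.
- The SD of 0.9 is that of a raw follow-up value. This is not stated.
- The correlation r between baseline and follow-up response is 0.3, 0.5 or 0.6. The documents give no value.

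**Step 1: reproduce 104.** The unadjusted two-sample formula is n per group = 2 × SD² × (1.960 + 0.842)² / d².

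2 × 0.81 × 7.85 / 0.1225 = 103.8, so 104 **per group** and 208 in total.

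Other simple readings do not give 104. A one-sided two-sample test needs 82 per group, and a one-sample or paired test needs 52. Taken as a total (52 per group), 104 gives 50.9% power in the unadjusted comparison.

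**Step 2: power of 150 children, unadjusted.** Power = Φ(d / (SD × √(2/n)) − 1.960).

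With n = 75: 0.35 / (0.9 × 0.1633) = 2.381, and Φ(2.381 − 1.960) = Φ(0.421) = 66.3%. The t-based value is 65.8%.

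**Step 3: add the baseline covariate.** Regression on the child's own baseline replaces the SD by SD × √(1 − r²). At r = 0.5 this is 0.9 × 0.866 = 0.779, a 25% cut in variance. Then 0.35 / (0.779 × 0.1633) = 2.750, and Φ(0.790) = 78.5%.

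| r (assumed) | Residual SD | Power, 75 per group | Gain (points) | n per group for 80% |
|---|---|---|---|---|
| 0 | 0.900 | 66.3% | – | 104 |
| 0.3 | 0.859 | 70.4% | 4.1 | 95 |
| 0.5 | 0.779 | 78.5% | 12.2 | 78 |
| 0.6 | 0.720 | 84.5% | 18.2 | 67 |

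**Step 4: attrition.** Section 11.2 uses 10% loss for the trial-wide 12-month outcomes. Borrowed here, it leaves 135 children (67.5 per group). Power is then 61.8% unadjusted and 74.2% at r = 0.5. The gain is almost unchanged, at 12.4 points.

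**The case against.** The strongest reply is that the plan has not chosen an inefficient analysis; it has chosen none. Immune responses are exploratory, carry no formal null hypothesis in section 11.1, and have no named test. A sample-size sentence does not bind the model, and a SAP is still to come. The sentence on no further adjustment is justified by expected balance between arms, which is a different matter from using an outcome's own baseline for precision. This stands in part. A reader might infer that the plan will compare raw means. The documents point that way but do not say so; what they show is that no adjusted model is stated.

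The SD may also not be raw. If 0.9 is already the SD of a change or of a residual, 75 per group still gives about 66% for that analysis, but the gains in the table do not follow. Equally, 104 could be a valid total if the SD is raw and the model is adjusted with a correlation near 0.71, since that needs 52 per group. The plan mentions neither a covariate nor a correlation, and 104 comes exactly from the unadjusted formula, so the per-group reading is much the more natural one.

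The comparison is undefined as well. The objective covers responses to infection and to treatment, which could include within-child change, where baseline is already used. And one correlation need not hold at 4 weeks, 6 months and 12 months, with treatment and possible reinfection in between. At r = 0.2 the gain is only about 2 points. These limits apply to the size of the gain. They do not weaken the case for naming the model.

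**Conclusion.** The point holds as a modest, nearly free improvement, together with a sizing error to correct. Section 11.4 states no baseline-adjusted model for the immune responses although every sub-study child is sampled before treatment. Section 11.2 gives 104 without saying that it is per group. With a raw SD of 0.9 and a 75/75 split, 150 children give about 66% power unadjusted, against the 80% targeted. Adjustment adds about 4, 12 or 18 points at assumed correlations of 0.3, 0.5 or 0.6.

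Three stronger readings should be avoided:

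- That the plan gives up 12 points of power. That figure belongs to a correlation of 0.5 alone, which the documents do not supply.
- That adjustment repairs the sizing. At 0.5 it reaches 78.5%, or 74.2% after 10% loss, and 80% would need 156 evaluable children.
- That the markers of environmental enteric dysfunction (EED, item 14) suffer the same measured loss. They too have baseline values and sit outside the adjusted model, but the plan gives no SD or difference from which a gain could be computed, and section 3.1.2.6 plans path modelling for them.

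The outcome is exploratory, so neither the primary conclusion nor the main morbidity comparisons are affected.

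**What to change.** In section 11.4 and the SAP, state that log10 immune responses at 4 weeks, 6 months and 12 months will be compared between randomised groups by linear regression, with the child's own baseline log10 response as covariate. Define the groups for each time point: the dosing-interval arms do not diverge until the six-month dose, so only dose can be compared at 4 weeks. The same covariate can be used for between-arm comparisons of EED markers that have a baseline value.

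In section 11.2, state that 104 is per group, say what the SD of 0.9 describes, and restate the power that 150 children give. If that power relies on the adjusted model, name the correlation assumed and show a range.

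The cost is a few sentences before database lock, with no new samples or visits. A child whose baseline assay is missing can be kept by mean imputation of the covariate with a missingness indicator.

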3. *Study Visit 3 (6 months post enrolment)* Six months (+/- 2 weeks) following visit one, subjects will return to the respective field laboratories. They will receive either the same dose of Praziquantel as received at Visit 1 or placebo as determined at baseline randomization. At this

visit, and before the study drug or placebo is received, blood will be drawn for follow up assessment of morbidity, and in depth measures of nutritional status. An ultrasound scan will be performed. Blood (7 ml) will be collected for the same subset of N=150 subjects for studies of immunological responses. Urine will be stored at this visit for future processing of CAA to monitor re-infection.

4. Study Visit 4, Close out. (12 months post enrollment) Twelve months (+/- 2 weeks) post enrollment and initial treatment, study subjects will return to the field laboratory. Prior to this visit they will be asked to provide three stool samples and one urine. At this visit, blood will be drawn for follow up morbidity studies and in-depth measures of nutritional status will be made. All children will be treated with Praziquantel and those infected with soil-transmitted helminths will be treated with albendazole 200 mg (12 – 24 month old children) or albendazole 400 mg (children over age two). A repeat ultrasound scan will be done before the participant is discharged from the study. If however, the ultrasound scan at six months revealed resolution of any pathology detected at baseline, there will be no repeat at discharge. Blood (7 ml) will be collected for the same subset of N=150 subjects for studies of immunological responses.

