11. STATISTICAL CONSIDERATIONS

11.1. Study Hypotheses

Primary outcome

The null hypothesis that there is no difference in cure rate assessed by microscopy at 4 weeks between children who received 40 mg/kg praziquantel and children who received 80 mg/kg praziquantel. This will be tested against the alternative hypothesis that there is a difference in cure rate at 4 weeks between children who received 40 mg/kg praziquantel and children who received 80 mg/kg praziquantel, and will be a superiority comparison.

Secondary outcomes

All secondary outcomes will be superiority comparisons, with alternative hypothesis of a difference in the outcome between the two sets of participants being compared.

For outcomes 1 to 5 below, the null hypothesis is that there is no difference in the outcome between children in the 40 mg/kg praziquantel group and children in the 80 mg/kg praziquantel group.

1. Mean egg reduction rate at 4 weeks
2. Schistosomal antigenic clearance assessed by CCA at 4 weeks
3. Schistosomal antigenic clearance assessed by CAA at 4 weeks
4. Prevalence of any adverse event within 3 hours of dosing

Adverse events will be classified by type. Adverse event types that occur with overall prevalence >5% or at prevalence >5% in either setting will also be tested for differences between trial arms.

5. (a) Prevalence of adverse event type 1 within 3 hours of dosing
(b) Prevalence of adverse event type 2 within 3 hours of dosing
(c) Prevalence of adverse event type 3 within 3 hours of dosing
continued for all adverse event types occurring with prevalence >5%

For secondary outcomes 6 to 13 below, two null hypotheses will be tested. The first null hypothesis is that there is no difference in the morbidity outcomes between children who received six-monthly praziquantel (either 40 mg/kg or 80 mg/kg) and children who received 12-monthly praziquantel (either 40 mg/kg or 80 mg/kg). The second null hypothesis is that there is no difference in the morbidity outcomes between children who received 40 mg/kg praziquantel (regardless of dosing schedule) and children who received 80 mg/kg praziquantel (regardless of dosing schedule).

6. Mean weight-for-height z-score at 12 months
7. Proportion with weight-for-height z-score at 12 months < -2
8. Mean MUAC-for-age z-score at 12 months
9. Proportion with MUAC-for-age z-score at 12 months < -2
10. Mean height-for-age z-score at 12 months
11. Proportion with height-for-age z-score at 12 months < -2

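### For the 12-month dosing-interval comparison, adding the pre-dose month-6 value to the month-0 covariate would probably gain precision at little cost; the planned adjustment is valid as it stands

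*Combined protocol and SAP*

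**What the plan says.** Section 11.4 sets one rule "For the secondary outcomes assessed at 6 and 12 months (anthropometry and anemia"): for continuous measures, "continuous outcomes will be compared between trial arms using linear regression, including the corresponding baseline measure as a covariate". Binary measures get the same covariate in a binary/logistic regression. The reason given is precision: "This will be done in order to improve the precision of the treatment effect estimate". No other adjustment is planned unless key baseline factors differ. The section does not separate the dose contrast from the interval contrast.

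Section 11.1 sets two null hypotheses for outcomes 6 to 13. One is about dose. The other is "no difference in the morbidity outcomes between children who received six-monthly praziquantel (either 40 mg/kg or 80 mg/kg) and children who received 12-monthly praziquantel". Every outcome in that list is at 12 months, for example "Mean weight-for-height z-score at 12 months".

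Under Table 1 and section 4.1, arms 1 and 2 share one regimen until the 6-month visit, and so do arms 3 and 4. At that visit, section 4.2.1 (Study Visit 3) says that "before the study drug or placebo is received, blood will be drawn for follow up assessment of morbidity", and the same sentence places the nutritional measures before the dose too. Section 7.5 lists weight, height and a complete blood count at this visit.

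**The concern.** The interval groups diverge only when the month-6 vial is given. A value measured just before that is a baseline for the interval question in the same sense as month 0 is for the dose question. It is six months from the outcome rather than twelve, so it will probably predict the outcome better. Section 11.4 adjusts for the sake of precision but leaves this value out.

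Section 11.2 calls 12-month weight-for-height the key secondary outcome and uses the interval contrast as its power example. The detectable difference there, 0.24, is close to the 0.23 that the section calls biologically relevant (stated for weight-for-age). At stake is how small an interval effect the trial can resolve with data it already plans to collect.

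**Working it through.** **Inputs from section 11.2.** 600 children less 10% attrition gives 540, or 270 per interval group. SD is 1 for weight-for-height z-score (WHZ) and 1.2 g/dL for haemoglobin. Power is 80%, two-sided 5%.

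**Reproducing the plan's figures.** Detectable difference = SD × (1.960 + 0.842) × √(2/270).
- WHZ: 1 × 2.8016 × 0.08607 = 0.241 (stated 0.24).
- Haemoglobin: 1.2 × 0.241 = 0.289 g/dL (stated 0.29).

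Both reproduce with no covariate, so the stated power does not depend on the choice of covariate.

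**Effect of the covariate.** One covariate with correlation r to the 12-month value multiplies the detectable difference by √(1 − r²). Write r0 for month 0 and r6 for month 6. The documents give neither, so these pairs are assumptions. The last column is 540 × (1 − r0²)/(1 − r6²): the children a month-0 analysis would need to match 540 with month 6.

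| r0 / r6 | WHZ: month 0 → month 6 | Haemoglobin, g/dL | Variance ratio (1 − r6²)/(1 − r0²) | Equivalent N |
|---|---|---|---|---|
| 0.3 / 0.5 | 0.230 → 0.209 | 0.276 → 0.251 | 0.75/0.91 = 0.82 | 655 |
| 0.5 / 0.7 | 0.209 → 0.172 | 0.251 → 0.207 | 0.51/0.75 = 0.68 | 794 |
| 0.6 / 0.8 | 0.193 → 0.145 | 0.231 → 0.174 | 0.36/0.64 = 0.56 | 960 |
| 0.7 / 0.85 | 0.172 → 0.127 | 0.207 → 0.152 | 0.2775/0.51 = 0.54 | 992 |

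**Both covariates.** With r06 the correlation between month 0 and month 6, R² = (r0² + r6² − 2·r0·r6·r06)/(1 − r06²). In the rows above, with r06 set to r0/r6 or to r6, adding month 0 to month 6 changes the WHZ figure by at most 0.001. The second covariate matters when the two predict equally well. With r0 = r6 = 0.6 a swap leaves 0.193 unchanged, but using both gives:
- r06 = 0.5: R² = (0.72 − 0.36)/0.75 = 0.48, and 0.241 × √0.52 = 0.174.
- r06 = 0.6: R² = (0.72 − 0.432)/0.64 = 0.45, and 0.241 × √0.55 = 0.179.

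**Simulation check** (540 children, 4,000 runs, r0 = 0.6, r6 = 0.8, r06 = 0.75, true interval effect 0.15):

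| Adjusted for | Mean estimate | Empirical SE | Power |
|---|---|---|---|
| month 0 | 0.148 | 0.069 | 57% |
| month 6 | 0.149 | 0.052 | 83% |
| both | 0.149 | 0.052 | 82% |

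All three are essentially unbiased; they differ in precision. In the same runs, a test of interval group on the month-6 outcome rejected 4.7% of the time, which is its chance rate.

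**Why the dose contrast must not use month 6.** Month 6 is after treatment for dose. If a dose effect of 0.15 is present at both months and r6 = 0.8, adjusting for month 6 leaves about 0.15 − 0.8 × 0.15 = 0.03. Simulation (2,000 runs) gave 0.030, against 0.149 with month-0 adjustment.

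**The case against.** The strongest reply is that nothing here is an error. Month-0 adjustment is valid, the stated detectable differences assume no covariate, and the planned model should do at least as well. That stands in full.

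The size of the gain is also assumed. A closer measurement usually predicts better, but the documents do not show it, and with a small gap between the correlations a swap gains little. Haemoglobin is less predictable still: sections 9.2.3 and 9.4 provide iron to anaemic children after baseline and repeat this at month 6, which could alter the two correlations differently. This stands too, and is why the figures are given as a range.

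The change has practical costs. A model that requires month 6 would drop children without that value. Covariates in a logistic model change the conditional odds ratio. Mid-upper-arm circumference (MUAC) is not among the month-6 measures in section 7.5, although section 7.3 does not list it at baseline either, so the planned covariate raises the same question. These points limit the fix but do not remove the case for it.

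A reader might go further and infer that the plan commits to an empty six-monthly v 12-monthly test at month 6, and that the covariate choice causes it. The documents do not support this. Section 11.1 lists the interval hypothesis at 12 months only. The loose wording is in section 11.4, which compares arms at both times, and in objective 3.1.2.3 (repeated in the Protocol Summary), which pairs dose and interval with both times. Such a test would be empty because of the visit schedule, whatever the covariate, and the month-6 dose comparison is meaningful.

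Section 4.2.1 describes randomisation at six months, whereas section 5.3.1 and Study Visit 3 fix the arm at baseline. These should be reconciled, but on either reading the interval groups have not diverged before the month-6 dose.

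**Conclusion.** This is a cheap improvement to the 12-month interval contrast, not a correction. For that contrast the month-6 value is a legitimate covariate that section 11.4 omits. On the assumed correlations, moving from month 0 to month 6 lowers the detectable WHZ difference from 0.230 to 0.209 at the weak end and from 0.172 to 0.127 at the strong end, or 18% to 46% less residual variance. A swap gains nothing if the correlations are equal; using both values then still helps, provided they are not redundant with each other.

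It would be wrong to infer that the interval comparison is biased or that its stated power fails: neither follows from the documents. What is certain is the timing of the measures and of the divergence. What is assumed is the correlations, and so the size of the gain.

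**What to change.** Section 11.4 leaves full details to a formal SAP to be finalised before database lock, so these points can be settled there:

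- **Interval contrast at 12 months** (weight-for-height, height-for-age, haemoglobin and anaemia): include the month-0 value, the pre-dose month-6 value and randomised dose. Do the same for MUAC only if it is measured at month 6.
- **Missing month-6 values:** keep these children in the analysis, for example with a mixed model that uses all pre-dose values and allows no interval difference before the month-6 dose.
- **Dose contrast:** fit a separate model adjusted for month 0 only. Do not report the dose coefficient from the interval model as the dose effect.
- **Binary outcomes:** pre-specify the covariate set for each contrast, because it defines the odds ratio.
- **Month-6 comparisons:** say in one sentence that they are by dose only, since the interval groups have not yet diverged. This aligns section 11.4, objective 3.1.2.3 and the Protocol Summary with section 11.1.

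The cost is two models instead of one and a missing-covariate rule. No new data are needed, except that month-6 MUAC must be confirmed.
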